4.6.1 Reporting Serious Adverse Events

All SAEs must be reported immediately to the Sponsor or designee (within 24 hours of awareness)Serious Adverse Event forms should be submitted to:

[name] PhD Axogen, Corp. Medical Affairs [name]

The site Investigator or designee may also be required to notify the IRB/Ethics Committee and appropriate regulatory body, as required per IRB/Ethics Committee guidelines. The SAE report and CRF should contain all adverse event information available at the time of event onset. As updates become available, the SAE report and CRF should be updated appropriately until the event is resolved including whether or not the event is required to be reported to the local/central IRB (based on local/central IRB reporting guidelines). The SAE form will collect data surrounding the event, e.g., the nature of the symptom(s), time of onset in relation to placement of study product, and whether or not treatment with study product was interrupted or discontinued. The site Investigator's assessment on the probable cause of the event will also be included.

Subjects experiencing a SAE or medical emergency should be examined by a physician as soon as possible. The physician in attendance should do whatever is medically necessary for the safety and well-being of the subject. The subject will remain under observation for as long as medically indicated in the opinion of the Investigator and/or attending physician. The SAE will be followed until resolved or until medically stabilized.

4.7 Unanticipated Adverse Device Effects (UADE)

An unanticipated adverse device effect (UADE) is defined as any serious adverse effect on health or safety or any life-threatening problem or death caused by, or associated with, a device, if that effect, problem, or death was not previously identified in nature, severity, or degree of incidence in the Investigational Plan or application (including a supplementary plan or application), or any other unanticipated serious problem associated with a device that relates to the rights, safety, or welfare of subjects.

4.7.1 Reporting of Unanticipated Adverse Device Effects (UADE)

The Investigator should report any unanticipated adverse device effects to the Sponsor and the IRB as soon as possible, but no less than 10 working days after the site Investigator first learns of the UADE. The Sponsor must immediately conduct an evaluation of the UADE and determine whether the UADE presents an unreasonable risk to the subject. If an unreasonable risk is concluded, the Sponsor shall terminate all or part of the investigation as soon as possible but no later that 5 working days after the Sponsor make the determination and no later than 15 working days after the Sponsor first learns of the effect.

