4.6 Serious Adverse Events

A Serious Adverse Event (SAE) is any untoward medical occurrence that occurs per the following definition:³⁹

- Results in death;
- Is immediately life threatening In the opinion of the site Investigator, the participant was at substantial risk of dying at the time of the event, or use or continued use of the device might have resulted in the death of the subject;
- Requires in-patient hospitalization or prolongation of existing hospitalization. Complications that occur during hospitalization are adverse events, and if a complication prolongs hospitalization, the event is considered serious. Emergency room visits that do not result in overnight hospital admissions should be evaluated for one of the other serious outcomes (e.g., life-threatening; required intervention to prevent permanent impairment or damage);
- Results in disability or Permanent Damage substantial disruption of a person's ability to conduct normal life functions, i.e., resulted in a significant, persistent or permanent change, impairment, damage or disruption in body function/structure, physical activities and/or quality of life;
- Results in a Congenital Anomaly/Birth Defect suspect that exposure to the device prior to conception or during pregnancy may have resulted in an adverse outcome in the child; or
- Requires Intervention to Prevent Permanent Impairment or Damage medical or surgical
 intervention was necessary to preclude permanent impairment of a body function, or prevent
 permanent damage to a body structure, either situation suspected to be due to the use of the
 device.
- Other Serious (Important Medical Events) when the event does not fit the other outcomes, but the event may jeopardize the subject and may require medical or surgical intervention

(treatment) to prevent one of the other outcomes. Examples include allergic brochospasm (a serious problem with breathing) requiring treatment in an emergency room, serious blood dyscrasias (blood disorders) or seizures/convulsions that do not result in hospitalization. The development of drug dependence or drug abuse would also be examples of important medical events.

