9. ETHICS AND RESPONSIBILITY

This study must be conducted in compliance with the protocol, FDA regulations, ICH and GCP Guidelines, ISO 14155:2011 and all other applicable regulatory requirements.

The study protocol and the written informed consent form must receive a favorable review and/or approval from the governing IRB/IEC with the responsibility to approve research for the study site. The site Investigator will not participate in the approval process of a clinical study he/she is conducting. If the site Investigator is an IRB/IEC member, the written approval must indicate such non-participation.

The site Investigator will submit study status reports to the IRB/IEC in accordance with local IRB/IEC requirements. The site Investigator must notify the IRB/IEC in writing of the interruption and/or completion of the study. The site Investigator must promptly report to the IRB/IEC all changes in research (protocol amendments) and will not make such changes without IRB/IEC approval except when necessary to eliminate apparent immediate hazards to human subjects. In these cases, the IRB/IEC must be notified with 5 working days of the change. The site Investigator will promptly report to the IRB/IEC all unanticipated problems involving risks to subjects or others. The site Investigator must maintain accurate and complete records of all correspondence written to and received from the IRB/IEC and must agree to share all such documents and reports with the Sponsor.

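### Protocol 4.7.1 writes the investigator's deadline for reporting an unanticipated adverse device effect as a minimum wait with no maximum, in conflict with the protocol's other reporting rules.

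*Protocol*

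**What the plan says.** Protocol 4.7.1 opens: "The Investigator should report any unanticipated adverse device effects to the Sponsor and the IRB", and gives the timing as "as soon as possible, but no less than 10 working days after the site Investigator first learns of the UADE". The rest of the section sets the sponsor's duties. It must evaluate the event at once. If it finds an unreasonable risk, it must terminate all or part of the investigation within 5 working days of that determination, and "no later than 15 working days after the Sponsor first learns of the effect".

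Three other provisions bear on the same events:

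- **Protocol 4.6.1 (SAE reporting):** "All SAEs must be reported immediately to the Sponsor or designee (within 24 hours of awareness". No exception is made for UADEs.
- **Protocol 4.7 (definition):** the main limb of the UADE definition covers "any serious adverse effect on health or safety or any life-threatening problem or death caused by, or associated with, a device", where the effect was not previously identified in the plan. A residual limb adds "any other unanticipated serious problem associated with a device that relates to the rights, safety, or welfare of subjects".
- **Protocol section 9 (IRB):** "The site Investigator will promptly report to the IRB/IEC all unanticipated problems involving risks to subjects or others".

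The SAP repeats the UADE definition in its section 6 but gives no reporting time limit, so it does not settle the matter.

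**The concern.** A reporting deadline should bound the delay from above. This one bounds it from below: as written, a report on day 3 breaches the limit and a report on day 60 meets it. The clause is an instruction that sites are expected to follow, not background text.

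What is at stake is when the sponsor hears of a serious, unforeseen problem with the device. The sponsor's evaluation cannot begin, and its outer limit for termination does not start to run, until it learns of the effect. Whatever delay the site clause permits comes on top. UADEs also form part of a primary safety endpoint (Protocol 3.5.1; SAP 9.3.1), so the rule concerns events that the trial sets out to capture.

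**Working it through.** No statistical figure is involved and the plan gives none to reproduce. The check sets the provisions side by side.

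**Inputs**

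| Rule | Source | Literal window after the site learns of the event |
|---|---|---|
| UADE, investigator to sponsor and IRB | Protocol 4.7.1 | 10 working days or later, no upper limit |
| SAE, investigator to sponsor | Protocol 4.6.1 | 0 to 24 hours |
| Unanticipated problems, investigator to IRB | Protocol section 9 | promptly, no figure |
| Sponsor's termination limit | Protocol 4.7.1 | up to 15 working days, counted from when the sponsor learns |

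**Step 1: within the sentence.** Reporting as early as possible and reporting no earlier than 10 working days cannot both be required. The word joining the two halves makes sense only if the second half is an outer limit on the first.

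**Step 2: within the section.** Both sponsor limits in 4.7.1 are ceilings. Only the investigator's limit runs the other way. That points to a slip in drafting, and the conclusion needs no outside regulation.

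**Step 3: a UADE that is also an SAE.** The main limb of the definition covers serious effects, life-threatening problems and deaths. Protocol 4.6 lists "Results in death" and immediately life-threatening events among its SAE criteria. Such an event falls under both rules for notifying the sponsor.

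- 10 working days = 2 weeks of 5 working days = 14 calendar days, assuming no holidays.
- 14 × 24 = 336 hours, against 24 hours: a ratio of 336 / 24 = 14.
- The windows (336 hours or later; 0 to 24 hours) do not overlap, so one notification to the sponsor cannot satisfy both.

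With the limit turned into a ceiling, the windows become 0 to 336 hours and 0 to 24 hours. A report within 24 hours then meets both.

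**Step 4: a UADE that is not an SAE.** The residual limb reaches problems that concern only subjects' rights, which need not meet any criterion in Protocol 4.6. The 24-hour rule does not apply to them, and 4.7.1 is the only explicit deadline to the sponsor. The permitted delay before the sponsor learns has no upper bound, so neither does the time to the end of its 15-working-day limit.

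**Step 5: the IRB.** The 24-hour rule covers the sponsor only; 4.6.1 leaves IRB timing to IRB guidelines. On the IRB side, the floor conflicts with the opening of its own sentence and with the prompt reporting in section 9.

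**The case against.** The strongest reply is that no sensible site would be misled. The sentence starts by asking for the earliest possible report, ceilings follow it, and section 9 asks for promptness. In addition, 4.6.1 says that SAEs must be reported, while 4.7.1 says only that UADEs should be. A UADE that is an SAE therefore reaches the sponsor within 24 hours in any case. Because the sponsor's 15-working-day limit runs from when it first learns of the effect, that SAE report already starts the clock. One could also treat the SAE report and the UADE report as two documents, the second filed later.

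Much of this stands. It lowers the practical risk for UADEs that are SAEs, and it shows that once the limit is a ceiling the two deadlines are compatible. It does not help a UADE that is not an SAE, which has no 24-hour report behind it. Nor should a safety deadline depend on readers reversing what it says.

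Four stronger readings are tempting, and the documents do not support them:

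- **Every UADE is an SAE.** The residual limb of the definition in 4.7 need not meet the SAE criteria.
- **This report is the only route to halting the study.** Protocol 3.10.3 separately allows termination when a serious or unacceptable risk comes to light, and 4.9 has the sponsor review safety information from any source.
- **The trial has no means of stopping, because SAP 8.3 states no stopping rules.** That is a statement in the analysis plan; Protocol 3.10.3 and 4.7.1 itself contain termination provisions.
- **The error costs 10 + 15 = 25 working days.** That sum is the cap from site awareness to the sponsor's limit once the clause is read as a ceiling. The literal clause has no cap, and for an event reported as an SAE the clock has started within 24 hours.

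**Conclusion.** The clause is wrong as written and should be corrected. The removal of text from the public documents does not explain it, since the sentence is complete.

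Its size differs by type of event. For UADEs that meet the SAE criteria, the contradiction is literal (10 working days at least, against 24 hours at most), but the SAE rule should limit the harm provided sites follow it. For UADEs outside those criteria, there is no upper limit on the delay before the sponsor's evaluation and termination clock begin. How many UADEs would be of that kind cannot be estimated from the documents.

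That a maximum was intended is an inference from the sentence and its neighbours, though a well-supported one. This is an inconsistency in a safety-reporting rule rather than a choice of design. Sample size, type I error and the efficacy estimate are untouched.

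**What to change.** In Protocol 4.7.1, restate the investigator's limit as a maximum: as soon as possible and no later than 10 working days after first learning of the UADE.

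Add one sentence: a UADE that also meets the SAE criteria in 4.6 remains subject to the 24-hour report to the sponsor in 4.6.1, and the 10 working days are the outer limit for the UADE report to the sponsor and the IRB. The added sentence is needed because correcting the limit alone would leave two different sponsor deadlines for one event, with nothing to say how they relate. It should not say that all UADEs are SAEs.

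The cost is one changed phrase and one new sentence, handled as an amendment under Protocol 12.1 and notified to sites. No data collection, analysis or sample size changes.

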4.8 Follow-up of Adverse Events

All adverse events ongoing at the final study visit will be followed by the site Investigator:

- until the adverse event has resolved; or
- until the subject is lost to follow-up; or
- until the adverse event is stabilized or deemed a permanent disease or condition.

"Resolution" of an AE occurs when the subject has returned to his/her baseline state of health or when the site Investigator does not expect any further improvement or worsening of the AE. On the last clinical study day, the investigator will instruct the subject to report any subsequent adverse event that the subject or the subject's physician believes might reasonably be caused by, or probably caused by, the study product. The site Investigator will continue to report any significant follow-up information to the Sponsor or designee.

All SAEs that occur up to 30 days following the subject's last study assessment must be reported immediately to the medical monitor.

4.9 Review of Safety Information

The Sponsor shall promptly review all information relevant to the safety of the study device or otherwise received by the Sponsor from any source, foreign or domestic, including information derived from any clinical or epidemiological investigations, animal investigations, commercial marketing experience, reports in the scientific literature, and unpublished scientific papers, as well as reports from foreign regulatory authorities.

5. STATISTICAL CONSIDERATIONS

Descriptive statistical methods will be used to summarize the data from this study. Unless stated otherwise, the term "descriptive statistics" refers to number of events (n), mean, median, standard deviation (SD), standard error, minimum, maximum, and coefficient of variation (CV) for continuous data and frequencies and percentages for categorical data. All data collected during the study will be included in data listings. Unless otherwise noted, the data will be sorted by subject number, and then by date within each subject number.

Unless specified otherwise, all statistical testing will be two-sided and will be performed using an overall significance (alpha) level of 0.05.

All statistical analyses will be conducted with the SAS® System, version 9.1.3 or higher.

5.1 Data Collection Methods

The data will be recorded on an approved Case Report Form (CRF). The CRF for this study may be either a paper CRF, or at Axogen's discretion, the data collection methods may be an electronic CRF,. All investigative site source documentation supporting the CRF data, such as laboratory or hospital records, physician dictations, nurse notes, any study-related subject logs, subject diaries and/or completed questionnaires must be readily available to verify entries in the CRF.

Any investigative site source document (including laboratory reports, hospital records, etc. subsequent to SAEs, etc.) electronically transmitted are to be de-identified and contain no subject identification information with the exception of a subject's assigned study ID. This will help to ensure subject confidentiality.

5.2 Statistical Analysis Plans

A statistical analysis plan (SAP) will be created and approved prior to the beginning of subject enrollment. This document will provide a more technical and detailed description of the proposed data analyses and statistical methods.

Test of non-inferiority and superiority of Axoguard® Nerve Cap compared to neurectomy with respect to VAS (visual analog scale) pain score will be conducted using closed testing procedures.

5.4 Sample Size Estimates A total of 101 subjects at up to 10 sites may be enrolled to control for site effects
For the pilot study, 15 evaluable subjects will first be selected to receive the open label Axoguard® Nerve Cap.
For the comparative study, 86 evaluable subjects will then be selected for enrollment.

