Number of Subjects per Treatment Group: Enroll approximately 15 evaluable subjects in the pilot study. Enroll approximately 86 additional subjects for the randomized comparative study.

Duration of Study: Up to 13 months including screening period.

Inclusion Criteria:

Potential Subjects must:

- 1. Be able and willing to provide documented informed consent prior to the conduct of any study procedures;
- 2. Be an adult male or non-pregnant female ≥ 18 years of age;
- 3. Report baseline pain scores of >65mm on a 100mm Visual Analog Scale (VAS) at screening;
- 4. Have a documented diagnosis of symptomatic neuroma of at least one interdigital nerve in the foot which cannot be repaired to a distal nerve end;
- 5. Must have the of the following:
 - Pain with at least 3 of the following characteristics: burning, sharp, shooting, electric, parasthesias, numbness, cold intolerance;
 - Symptoms in a defined neural anatomic distribution
 - History of nerve injury or suspected nerve injury Must have at least 1:
 - Positive response to local anesthetic injection
 - US or MRI confirmation of neuroma
- 6. Be candidates indicated for surgery to address a symptomatic neuroma;
- 7. Have sufficient healthy soft tissue available to adequately cover the Axoguard® Nerve Cap;

- 8. In the surgeon's opinion, be likely to achieve complete resection of the symptomatic neuroma and be able to undergo implantation with the Axoguard[®] Nerve Cap or complete the neurotomy procedure in the control group;
- 9. Be willing and able to comply with all aspects of the treatment and evaluation schedule over a 12-month duration.

Exclusion Criteria:

Potential subjects must not:

- 1. Have undergone surgical treatment of pain from symptomatic neuroma in the target nerve(s)on three or more occasions;
- 2. Have biomechanical pathology and associated pain (such as plantar fasciitis, bursitis, sesamoid bone pain, tendinitis, etc);
- 3. Have a life expectancy of less than 12 months;
- 4. Have a history of or planned radiotherapy in the area of the end-neuroma;
- 5. be contraindicated for soft tissue implants.; this includes but is not limited to any pathology that would limit the blood supply; compromise healing or indicate the presence of a local infection;
- 6. Have a history of chronic ischemic conditions of the extremity;
- 7. Have a diagnosis of type 1 Diabetes Mellitus; or uncontrolled Type 2 Diabetes Mellitus (at the discretion of the investigator);

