3. STUDY DESIGN

3.1 Description of Design

This is a multicenter, prospective, randomized, controlled, subject blinded comparative parallel group study in patients presenting with symptomatic neuroma (verified by diagnostic block or imaging (US or MRI confirmation) with a baseline pain level of \geq 65 mm on a 100 mm Visual Analog Scale (VAS) during screening. Fifteen (15) pilot subjects will receive the Axoguard® Nerve Cap in the pilot phase of the study. In the comparative phase of the study, approximately 86 adult subjects meeting inclusion/exclusion criteria will be centrally randomized in a 1:1 ratio to receive either Axoguard® Nerve Cap or neurectomy. This study design overview is found in Figure 3.1. This study is intended to collect post-operative data as well as physician experience surveys on the clinical use of Axoguard® Nerve Cap to evaluate its safety and performance as compared to subjects receiving neurectomy.

Figure 3.1. Study Design

This study will consist of a total of 8 visits

This study will be conducted in

accordance with the FDA regulations21 CFR Parts 50 and 56 and current cGCP requirements as described in the ISO 14155:2011 standards, applicable IRB regulations.

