3.4.4.4 Subject Replacement

Once a subject is randomized, they may not be replaced.

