3.10.2 Subject Discontinuation

Subjects may end their participation in the study at any time for any reason(s). The reason for discontinuation should be documented.

Early termination will be defined as any post-randomization study termination prior to completion of the Month 12 assessment. Subjects that terminate early will not be replaced. Reasons for early termination will be tabulated by center as well as by the study overall.

Subjects that have not completed the study and who are unable to be contacted or for whom the reason for discontinuation is unknown will be considered "lost to follow-up". The site will make three attempts to contact the subject by either telephone, certified mail or by an alternative method. The site may continue to try to achieve appropriate follow-up until the 12 month follow-up visit . Because these follow-ups typically only require the collection of pain assessments, Quality of Life assessments, Daily Pain Medication Diary, and Daily Pain Diary, the assessments may be captured via phone or returned to the site electronically or by mail.

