7.1. Sample Size and Power

A total of 101 participants (15 pilot; 86 comparative/randomized) at up to 20 sites will be enrolled.

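### Protocol 5.4 labels as evaluable the same 86 subjects that the rest of the plan enrols or randomises, so 86 evaluable is met only with zero loss

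*Protocol*

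**What the plan says.** Protocol 5.4 gives the size of each phase in evaluable subjects. For the randomised phase: "For the comparative study, 86 evaluable subjects will then be selected for enrollment". For the pilot: "For the pilot study, 15 evaluable subjects will first be selected to receive the open label Axoguard® Nerve Cap". The same section sets the overall number: "A total of 101 subjects at up to 10 sites may be enrolled to control for site effects".

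Elsewhere 86 is a starting number:

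- Protocol synopsis: "Enroll approximately 86 additional subjects for the randomized comparative study".
- Protocol 3.1: "approximately 86 adult subjects meeting inclusion/exclusion criteria will be centrally randomized in a 1:1 ratio".
- SAP 7.1: "A total of 101 participants (15 pilot; 86 comparative/randomized) at up to 20 sites will be enrolled". SAP section 4 likewise has 86 participants being randomised.

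On replacement, Protocol 3.4.4.4 says "Once a subject is randomized, they may not be replaced", and Protocol 3.10.2 says "Subjects that terminate early will not be replaced". SAP 8.3 also rules out replacing participants who discontinue.

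Neither document defines 'evaluable'. The nearest defined set is the ITT population (Protocol 5.5.1, SAP 7.4.1), which requires treatment and at least one post-baseline efficacy assessment.

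**The concern.** An evaluable number is normally what remains after losses, and the number randomised is set higher to allow for them. Here the two are equal. The primary endpoint of the comparative phase is VAS change at 12 months (Protocol 3.5.2, SAP 9.1.1), and the plan itself foresees loss. Protocol 3.4.4.3 and 3.10.2 cover withdrawal, early termination and loss to follow-up. Protocol 3.4.4.1 allows participation to end when contralateral surgery cannot be done by day 270. SAP 7.3 provides for imputing the primary endpoint.

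At stake is what the stated size means. A reader of 5.4 would expect 86 subjects with usable primary data. A reader of SAP 7.1 would expect 86 randomised and some smaller number observed at Month 12. The study report could then be judged against an evaluable target that the design supports only with perfect retention, and any precision or power attached to 86 would be read against the wrong count.

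**Working it through.** **1. Is there any allowance above the evaluable target?** Inputs: 15 and 86 evaluable and a total of 101 (Protocol 5.4); 15 pilot and 86 randomised (SAP 7.1).

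15 + 86 = 101. The sum of the two evaluable targets equals total enrolment, so the allowance is 101 − 101 = 0.

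**2. Chance that all 86 remain evaluable.** The documents show no loss rate, so d is an assumption. With independent losses, P = (1 − d)^86.

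| Assumed loss d | P(all 86 evaluable) |
|---|---|
| 1% | 0.42 |
| 2% | 0.18 |
| 5% | 0.012 |
| 10% | 0.0001 |

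**3. Expected evaluable number if 86 are randomised**, 86 × (1 − d):

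| Assumed loss d | 86 × (1 − d) | Rounded |
|---|---|---|
| 5% | 81.7 | 82 |
| 10% | 77.4 | 77 |
| 15% | 73.1 | 73 |
| 20% | 68.8 | 69 |

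**4. Could 86 already include attrition?** The plan's 86 cannot be reproduced, because no effect size, SD, power or margin is visible. Working backwards, 77/0.90 = 85.6 and 73/0.85 = 85.9 both round up to 86, and 34 per arm/0.80 = 42.5 rounds up to 43 per arm. Each fits, but the documents confirm none of them. If one is right, 'evaluable' is the wrong word in 5.4. If none is, the number randomised carries no allowance. Section 5.4 needs correcting either way.

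**5. Illustrative effect on power, if 86 evaluable is what the calculation needs.** Inputs: 43 per arm from 1:1 allocation; two-sided alpha 0.05 (Protocol section 5); assumed 80% power at 43 per arm; two-sample t-test. The standardised difference giving 80% power at 43 per arm is 0.611 SD. Holding that difference and using 43 × (1 − d) per arm:

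| Loss | Per arm | Power | Difference detectable at 80% | At an assumed SD of 25 mm |
|---|---|---|---|---|
| 0% | 43 | 80% | 0.61 SD | 15.3 mm |
| 10% | 38.7 | 75.6% | 0.65 SD | 16.1 mm |
| 15% | 36.55 | 73.2% | 0.66 SD | 16.6 mm |
| 20% | 34.4 | 70.5% | 0.69 SD | 17.1 mm |

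For scale, Protocol 1.1 gives 14 to 20 mm as the usual minimum clinically significant VAS difference. These rows give no credit for subjects with earlier VAS data but none at Month 12.

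**The case against.** **'Evaluable' is undefined.** In 5.4 the word describes subjects being selected, so it may mean no more than eligible. If it means ITT membership, loss could be very small: randomisation is intra-operative and VAS is first repeated at Week 2. This stands as far as it goes, and it means the size of any shortfall depends on the definition. It does not remove the mismatch, since even ITT membership needs one post-baseline assessment and a randomised subject who misses it is not replaced.

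**The sample-size basis is not visible.** The text of Protocol 5.3 is absent, and 5.4 and SAP 7.1 hold only fragments, which fits blacked-out text. The hidden part may state attrition or power. A reader might infer that power at Month 12 will be lower than planned. The documents do not support that: 86 may already include attrition, and the mixed model on observed data (Protocol 5.7.4) and imputation of the primary endpoint (SAP 7.3) keep partly observed subjects in the analysis. Protocol 3.10.2 also lets assessments be captured by phone, mail or electronically.

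**The size is approximate, and screen failures sit outside it.** A reader might infer that 86 evaluable cannot be reached, or that nobody is ever replaced. Both go too far. Zero loss would reach it, 'approximately 86' in the synopsis and 3.1 leaves slight room, and the protocol's replacement bar covers randomised subjects. Screen failures occur before randomisation and do not use up the 86. Still, 'approximately' is not a stated allowance, and 5.4 and SAP 7.1 omit it.

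**It is only one word, and the SAP already uses the right one.** True, and that is why the remedy is small.

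**Conclusion.** The contradiction is established on visible text. Protocol 5.4 states 86 evaluable comparative subjects within a total of exactly 15 + 86, while Protocol 3.1 and the SAP make the same 86 the number randomised, and no randomised subject is replaced. The evaluable size is met only with zero loss. This holds whatever the hidden justification contains, because an 86 that already allowed for attrition would not be an evaluable number.

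The size of the shortfall depends on the meaning of 'evaluable' and on the loss rate. For Month 12 completers, the expected number is about 82 to 69 over assumed losses of 5 to 20%. Under the ITT definition it could be close to 86. The fall in power from 80% to roughly 70–76% at 10 to 20% loss illustrates one reading and is not a demonstrated departure from plan. The same labelling question touches the 15 evaluable pilot subjects, who are likewise counted one for one in the 101.

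**What to change.** In Protocol 5.4:

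1. Change the label on 86 from evaluable to randomised, matching SAP 7.1.
2. Define 'evaluable', for example as having VAS observed at Month 12, and use the same definition in the SAP.
3. State the loss rate assumed and the expected evaluable number that follows from it.
4. If the sample-size calculation needs 86 evaluable, restate the power or detectable difference for the lower number. If 86 already includes attrition, say so; then only the label and the expected evaluable number change.

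The cost is wording in one protocol section, with the definition carried into the SAP. No extra enrolment is needed and no analysis changes. The only downside is that a stated power or detectable difference may become slightly less favourable.
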